2.1.5 Immunogenicity endpoints

2.1.5.1 Anti-drug (efpeglenatide) antibody

Blood samples are taken to assess the Anti-drug antibody (ADA) status (positive/negative) and level (titer). Mapping the ADA epitopes of confirmed positive samples to different moieties of efpeglenatide, (ie, HMC001, exendin-4 and polyethylene glycol (PEG)) and cross-reactivity to endogenous GLP-1 (positive/negative), endogenous glucagon (positive/negative), neutralizing capacity of ADAs will also be evaluated for efpeglenatide groups in serum, at the time points specified in protocol.

Subjects with pre-existing ADAs are those with a positive ADA at Baseline. Non-missing post-Baseline titer values are deemed treatment-induced ADAs if the subject had a negative or missing ADA status at Baseline. Treatment-boosted ADAs are defined as a post-Baseline minimum 2-fold increase in Baseline titer value for subjects with pre-existing ADA at Baseline.

Persistent ADA response is defined as: Treatment-induced or treatment-boosted ADA detected at two or more sampling time points during the study (ie, including post-study observation period), where the first and last treatment-induced or treatment-boosted ADA samples (irrespective of any negative samples in between) are separated by at least 16 weeks.

Transient ADA response is defined as: (1) Treatment induced or treatment-boosted ADA detected only at 1 sampling time point during the study (excluding the last sampling time point); or (2) Treatment induced or treatment-boosted ADA detected at 2 or more sampling time points during the study, where the first and last treatment-induced or treatment-boosted ADA samples (irrespective of any negative samples in between) are separated by a period less than 16 weeks and the last time point is ADA-negative.

Indeterminate ADA response: Only the last sampling time point is treatment-induced or treatment-boosted ADA sample and all previous samples are negative.

The data will be presented as:

- Number of participants by ADA status (positive/negative) at scheduled visits
- Number of participants with treatment-induced ADAs (among the participants with ADA negative or missing at Baseline)
- Number of participants with treatment-boosted ADAs (among the participants with ADA positive at Baseline)
- ADA titer at scheduled visits
- Number of participants by ADA cross-reactivity to endogenous GLP-1 (positive/negative) at scheduled visits
- Number of participants by ADA cross-reactivity to endogenous glucagon (positive/negative) at scheduled visits

- Number of participants with ADAs directed against PEG linker of efpeglenatide at scheduled visits
- Number of participants with ADAs directed against the HMC001 moiety of efpeglenatide at scheduled visits
- Number of participants with ADAs directed against the exendin-4 moiety of efpeglenatide at scheduled visits
- Number of participants by status of anti-efpeglenatide neutralizing antibodies (positive/negative) at scheduled visits
 - Number of participants by status of neutralizing antibodies against endogenous GLP-1 (positive/negative) at scheduled visits
 - Number of participants by status of neutralizing antibodies against endogenous glucagon (positive/negative)

2.1.6 Pharmacokinetic endpoints

Pharmacokinetic variables include the concentration of efpeglenatide in the efpeglenatide groups:

- Serum C_{trough} of efpeglenatide at pre-dose (Weeks 4, 12, 24, 30);
- Serum concentration of efpeglenatide at post-dose (either 4 days [± 1 day] after first IMP dose, 4 days [± 1 day] after 4th dose, or 4 days [± 1 day] after 12th dose in a subset of participants). All valid samples collected will be sent to the laboratory to be analyzed, even if out of the specified window.

2.1.7 Pharmacodynamic/genomics endpoints

Pharmacodynamic parameters are not evaluated in this study.

2.2 DISPOSITION OF PARTICIPANTS

This section describes participants' disposition for both participant study status and the participant analysis populations.

Screened participants are defined as any participants who signed the informed consent form.

Randomized participants consist of all participants with a signed informed consent form who have had a treatment kit number allocated and recorded in the IRT database, regardless of whether the treatment kit was used.

The total number of participants in each of the following categories will be presented in the clinical study report using a flowchart diagram or summary table:

- Screened participants;
- Screen failure participants and reasons for screen failure;

- Nonrandomized but treated participants;
- Randomized participants;
- Randomized but not treated participants;
- Randomized and treated participants;
- Participants who have completed the 30-week core treatment period as per protocol;
- Participants who did not complete the 30-week core treatment period, and main reasons for permanently treatment discontinuation;
- Participants who have completed the whole study treatment period including the 26-week extension period as per protocol;
- Participants who did not complete the whole study treatment period, and main reason for permanent treatment discontinuation;
- Participants who completed the study as per protocol;
- Participants who discontinued the study by main reason for permanent study discontinuation;
- Status at last study contact.

For all categories of participants (except for the screened, screen failure and nonrandomized but treated categories) percentages will be calculated using the number of randomized participants as the denominator. Reasons for treatment and study discontinuation will be supplied in tables giving numbers and percentages by treatment group. Number and percent of participants: screened, screen failed, randomized, randomized and treatment, ended treatment prematurely, and ended study prematurely will be provided by treatment group within each country and site as applicable.

List of participants who discontinued treatment and/or study will be provided with reasons for discontinuation, including reasons related to COVID-19.

Kaplan-Meier cumulative incidence of early IMP, premature discontinuation of treatment due to AE and study discontinuation will be provided.

Additionally, the following analysis populations will be summarized in a table by number of participants in the randomized population.

- Efficacy population: intent-to-treat (ITT) population
- Safety population
- ADA population
- Pharmacokinetics population

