#### **7.1.1 Permanent discontinuation**

Permanent intervention discontinuation is any intervention discontinuation associated with the definitive decision from the Investigator not to re-expose the participant to the IMP at any time during the study, or from the participant not to be re-exposed to the IMP whatever the reason.

The participants may withdraw from treatment with IMP if they decide to do so, at any time and irrespective of the reason. Participants should discuss stopping study medication with the site before doing so in order that questions can be addressed, concomitant therapy can be adjusted if needed, and a follow-up assessment arranged. All efforts should be made to document the reasons for treatment discontinuation and this should be documented in the e-CRF.

A participant should withdraw from treatment with IMP in case of the following:

- Intercurrent condition that requires discontinuation of IMP: eg, laboratory abnormalities (see decision tree and general guidance for the follow-up of laboratory abnormalities in Appendix 5 [[Section 10.5.1](#)]), diagnosis of acute pancreatitis confirmed by gastroenterologic evaluation and imaging, unless a clear cause unrelated to IMP is confirmed and the participant has recovered from pancreatitis (see Appendix 5 [[Section 10.5.2](#)]), or calcitonin value  $\geq 50$  pg/mL (see Appendix 5 [[Section 10.5.3](#)])
- If, in the Investigator's opinion, continuation with the administration of IMP would be detrimental to the participant's well-being
- Pregnancy (in female participants)
- Confirmed intolerance to the allocated dose of IMP

- Any code breaking requested by the Investigator
- At the specific request of the Sponsor

As all data until the scheduled date of study completion will be used in statistical analyses, it is important to collect data for all participants, under treatment or not, during the 56 weeks of the study. A high rate of missing data could jeopardize efficacy results of the study. See the SoA ([Section 3.1](#)) for data to be collected at the time of intervention discontinuation and follow-up and for any further evaluations that need to be completed.

Any abnormal laboratory value or ECG parameter will be immediately rechecked for confirmation (as soon as possible, preferably within 24 hours) before making a decision of permanent discontinuation of the IMP for the concerned participant.

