Proportions of participants who used rescue therapy during the treatment period until Week 30 and Week 56 will be compared by treatment group using a CMH test stratified by the randomization stratum of Screening HbA1c ($<8.0, \geq 8.0\%$) and Visit 3 (Baseline, Day 1) BMI ($<30, \geq 30 \text{ kg/m}^2$) in ITT population.

Time to initiation of rescue therapy (weeks)

Time to initiation of rescue therapy is defined as the time from the date of randomization to the date of first rescue therapy in weeks. Participants who did not take any rescue therapy during the study will be censored at the date of study completion/discontinuation. The curve of the cumulative incidence of participants with rescue initiation will be estimated using Kaplan-Meier method by study treatment group.

Patient reported outcome

The Patient Qualitative Assessment of Treatment version 2 (PQATv2) is intended for the collection of participant-perceived benefit-risk of glucose-lowering treatment with efpeglenatide. The participants will be asked to complete it from home just before the on-site visits planned at Weeks 30 and 56. If a participant discontinues treatment with IMP during the treatment period, the participant will be asked to complete the PQATv2 at the time of discontinuation.

The analysis of participant-reported outcome (PRO) endpoints will be descriptive with no formal testing. For categorical data, frequency and percentage will be provided by treatment group and overall at scheduled visits. Participants' answers to the open-ended questions of PQATv2 (items #1, 3 and 5) will be analyzed qualitatively and quantitatively, as relevant, using appropriate data analysis software. The analysis method for the open-ended questions will be provided in a separately and the analyses results will not be included in the CSR.

Other exploratory analysis

- Analysis to investigate whether the HbA1c decrease depends on the decrease in weight will be assessed by scatter plots of HbA1c reduction versus weight loss. A cumulative distribution plot will be provided for each of changes in HbA1c and in body weight from Baseline to Week 30 and 56.
- Proportion of participants with HbA1c <7.0% at Week 30 and 56 with no severe or documented symptomatic hypoglycemia will be assessed by number of participants and percentage by treatment group.

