- The frequency of TEAEs over time will be provided for nausea, vomiting, and diarrhea, using weekly time intervals through Week 8 and then every 4 weeks through Week 56, ie, [0-1] week, [1-2] weeks, [2-3] weeks, [3-4] weeks, etc. In each time interval, the numerator in the calculation of percentages will be the number of participants with at least 1 TEAE occurring in this time interval. Two types of analyses will be included: (1) only

the first event will be counted for each participant and all recurrent events will not be included, and the denominator for the calculation of percentages will be the number of participants at risk at the beginning of the time interval who did not experience a first event in the preceding intervals; and (2) the recurrent events in subsequent intervals will be counted once for each participant in the numerator of the corresponding interval, and the denominator for the calculation of percentages will be the number of participants at risk at the beginning of the time interval. A histogram of the frequency over time (by weekly intervals) will also be presented as appropriate.

- All TEAEs by BMI subgroup (< 30, \geq 30 kg/m²)
- All TEAEs by Anti-Efpeglenatide Antibody Status (Positive, Negative)

Analysis of all treatment emergent serious adverse event(s)

- All serious TEAEs by primary SOC, HLGT, HLT, and PT, showing the number (%) of participants with at least 1 serious TEAE

All serious TEAEs related to IMP, by primary SOC and PT, showing the number (%) of participants with at least 1 serious TEAE.

Analysis of all treatment-emergent adverse event(s) leading to treatment discontinuation

All TEAEs leading to treatment discontinuation, by primary SOC, HLGT, HLT, and PT, showing the number (%) of participants

Analysis of adverse events of special interest and adverse events requiring specific monitoring

Adverse events of special interest (AESI) and adverse events requiring specific monitoring (AERSM) include AE defined in [Section 2.1.4](#) and the criteria of AESI and AERSM are in [Table 3](#).

Table 3 - Criteria for AESI and AERSM

AE Grouping	Criteria
AESI	
Pregnancy	“Pregnancy” or “Partner pregnancy” checked
Symptomatic Overdose	“Overdose” checked and symptomatic (AEOVSYMP) = “Yes”
Increase in ALT >3 ULN	“ALT Increase” checked and Yes to the question “Is the event an AESI?” in eCRF form “Adverse Events”
AERSM	
Severe GI event	AE severity = “severe” using Gastrointestinal disorders CMQ

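### The curve for treatment discontinuation due to AE is planned as a Kaplan-Meier cumulative incidence with no competing event or censoring rule, so it can overstate that risk

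*SAP*

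**What the plan says.** The disposition section of the SAP (2.2) plans time-to-event displays in one sentence: "Kaplan-Meier cumulative incidence of early IMP, premature discontinuation of treatment due to AE and study discontinuation will be provided". I read this as three curves: all-cause IMP discontinuation, IMP discontinuation due to AE, and study discontinuation. No time origin, population, censoring rule or competing event is given for any of them.

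The same section plans crude displays: "Reasons for treatment and study discontinuation will be supplied in tables giving numbers and percentages by treatment group". For these, "percentages will be calculated using the number of randomized participants as the denominator". SAP 2.4.5.1 adds "All TEAEs leading to treatment discontinuation, by primary SOC, HLGT, HLT, and PT, showing the number (%) of participants".

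Protocol 7.1.1 defines permanent discontinuation as a definitive decision by the investigator, "or from the participant not to be re-exposed to the IMP whatever the reason". It allows routes that need not involve an AE: "The participants may withdraw from treatment with IMP if they decide to do so, at any time and irrespective of the reason". It also lists code breaking and Sponsor request, and SAP 2.2 expects some reasons related to COVID-19.

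The only explicit time-to-event censoring rule I find in the SAP is for rescue therapy (2.4.4.4): "Participants who did not take any rescue therapy during the study will be censored at the date of study completion/discontinuation".

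**The concern.** For an all-cause curve, one minus Kaplan-Meier is a proper cumulative incidence, because no other reason for stopping can get in first. A curve for one reason is different. Someone who has permanently stopped IMP by own choice has no remaining chance of stopping it for an AE. Kaplan-Meier in its ordinary form censors that person, which amounts to assuming that he or she would have gone on to stop for an AE at the same rate as those still on drug. The result answers what would happen if nobody stopped for any other reason. That is not the cumulative incidence the SAP names.

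Two things are at stake. The clinical study report could show two different figures for AE discontinuation in one section, with no text to explain the gap. And the excess depends on how often other-reason stops come first, so a comparison of doses with placebo on this curve can shift if that rate differs between arms. Tolerability by dose is of interest here, since protocol 4.3 describes nausea and vomiting as dose related.

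**Working it through.** The documents state no figure for this curve and no discontinuation rates, so there is nothing to reproduce and every rate below is an assumption.

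**Inputs.** Treatment lasts 56 weeks (SAP 1.1). Let *a* be the true proportion stopping IMP for an AE by Week 56, and *b* the proportion stopping for any other reason. Suppose other-reason stops are censored.

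**Constant cause-specific hazards.** The total cumulative hazard is L = -ln(1 - a - b), and the AE share of it is L × a/(a + b). Hence

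1 - KM = 1 - (1 - a - b)^(a/(a + b)), while the true cumulative incidence is *a*.

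For example, a = 10% and b = 10% give 1 - 0.80^0.5 = 10.56%. With a = 10% and b = 20% it is 1 - 0.70^(1/3) = 11.21%.

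Week 56 value of 1 - KM (%):

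| True AE stops | Other 5% | Other 10% | Other 15% | Other 20% |
|---|---|---|---|---|
| 2% | 2.05 | 2.11 | 2.17 | 2.23 |
| 5% | 5.13 | 5.27 | 5.43 | 5.59 |
| 10% | 10.27 | 10.56 | 10.87 | 11.21 |
| 15% | 15.41 | 15.85 | 16.33 | 16.86 |

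The excess runs from 0.05 to 1.86 points, a relative excess of about 3% to 12%, and is below 1 point in 13 of the 16 cells. With b = 0 it is zero. As an extreme, 15% AE and 30% other stops give 18.07%.

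**Early AE stops.** Now place all AE stops evenly in weeks 0-8 and spread other stops evenly over 56 weeks. Only other stops before Week 8 matter, so *b* in the formula becomes b × 8/56. For 10%/10%: b × 8/56 = 1.43%, and 1 - 0.8857^0.875 = 10.07%. Likewise 10%/5% gives 10.04%, 15%/10% gives 15.11% and 2%/20% gives 2.03%. The excess is 0.03 to 0.11 point.

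**Arm contrasts, constant hazards.** The true difference is 8.0 points (10% active, 2% placebo); differences are taken before rounding.

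| Other stops, active | Other stops, placebo | Difference shown by 1 - KM |
|---|---|---|
| 10% | 10% | 8.45 |
| 5% | 20% | 8.03 |
| 10% | 20% | 8.32 |
| 15% | 5% | 8.82 |

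If both arms have the same rates (5% AE, 10% other), the excess is identical and the difference stays 0. Ratios can move when differences do not. With 6 mg at 10%/10% and placebo at 3%/30%, the curves end at 10.56% and 3.58%: a ratio of 2.95 against a true 3.33, but a difference of 6.98 points against a true 7.0.

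**Alternative censoring.** If other-reason stops were kept in the risk set to the end of follow-up, one minus Kaplan-Meier would equal the crude cumulative incidence and the excess would vanish. Participants who also left the study would still be censored when they left.

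**The case against.** The strongest reply is that the SAP never says other-reason stops are censored. Its one written rule, for rescue, censors at study completion or discontinuation, and protocol 7.1 and 7.1.1 want participants who stop IMP to stay in the study. Under a rule of that type there is no overstatement for those who stay. This is correct, and it limits the point: the censoring is inferred from the usual meaning of the named estimator. But the rescue rule is not applied to this curve, and two different curves fit the same sentence.

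Second, nothing depends on the curve. SAP 2.4.5 calls the safety analysis essentially descriptive, no test or decision uses this display, and the by-reason and TEAE tables already give the crude proportion without this bias. This stands, and is why the point is minor.

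Third, constant hazards may exaggerate the effect. Protocol 2.3 and 4.3 describe nausea and vomiting as rising after the first injection and then falling, within about 2 to 4 weeks according to 2.3. If AE stops follow that course, the excess nearly disappears, as the early-stop cases show. This also stands, although the timing of AE stops is itself an assumption.

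A smaller point: pregnancy is an AE of special interest (protocol 8.3), so a pregnancy stop may be coded as an AE stop. It is not a safe example of a competing event.

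**Conclusion.** The point holds as a minor one. The SAP names Kaplan-Meier as the estimator of a cumulative incidence for one reason among several, the other reasons preclude the event, and no rule resolves this. On the ordinary reading the curve can exceed the proportion who stop for an AE. Under the assumed rates the excess is about 0.05 to 1.9 points with constant hazards, and about 0.1 point or less with AE stops in weeks 0-8 and other stops of 10-20%. In an arm of about 100, one point is one participant.

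A reader might infer more: that the curve overstates the risk in every arm, by different amounts, and so distorts the ranking of the doses. The documents do not support that. They give no discontinuation rates by arm. The excess is zero if no other-reason stop precedes an AE stop, and equal between arms with equal rates and timing. Different amounts are possible, not shown. The two all-cause curves do not share this problem, provided the handling of death is stated.

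**What to change.** In SAP 2.2, keep Kaplan-Meier for all-cause IMP discontinuation and all-cause study discontinuation. For IMP discontinuation due to AE, specify the Aalen-Johansen cumulative incidence function. The competing events are permanent IMP discontinuation for any other reason and death, with censoring at treatment completion. State the time origin (randomization or first injection), the population, and whether a fatal AE counts as the event or as competing.

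The end value of the curve will then match the disposition percentages, provided that both use the same population and reason coding and nobody is censored before completing treatment. If the sponsor prefers to keep Kaplan-Meier, the lesser remedy is to write the censoring rule and label the curve as a cause-specific one minus Kaplan-Meier, not a cumulative incidence.

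The cost is a sentence or two of SAP text and slight extra programming. No new data are needed, and the primary analysis, alpha and sample size do not change.

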2.2.1 Protocol deviations

All significant deviations, potentially impacting efficacy analyses, randomization, and drug-dispensing irregularities, as well as other selected significant deviations will be summarized

in tables giving numbers and percentages of deviations by treatment group in randomized population. Listing of participants with at least one significant deviation will be provided.

Additionally, participants with any protocol deviations due to COVID-19 will be summarized and listed separately.

2.3 ANALYSIS POPULATIONS

Participants treated without being randomized will not be considered randomized and will not be included in any efficacy population.

The randomized population includes any participant who has been allocated to a randomized treatment regardless of whether the treatment kit was used.

For any participant randomized more than once, only the data associated with the first randomization will be used in any analysis population. The safety experience associated with any later randomization will be assessed separately.

The safety experience of participants treated and not randomized will be reported separately, and these participants will not be in the safety population.

2.3.1 Efficacy populations

The efficacy analysis population will be the ITT population.

2.3.1.1 *Intent-to-treat population*

The ITT population is defined as all randomized participants, irrespective of compliance with the study protocol and procedures analyzed, according to the treatment group allocated by randomization.

2.3.2 Safety population

The safety population is defined as:

- Randomized population who actually received at least 1 dose or part of a dose of the IMP, analyzed according to the treatment actually received

In addition:

- Nonrandomized but treated participants will not be part of the safety population; however, their safety data will be presented separately.
- Randomized participants for whom it is unclear whether they took the IMP will be included in the safety population as randomized according to their planned treatment.
- For participants receiving 1 or more injections of efpeglenatide during the trial, regardless of being assigned to the efpeglenatide groups or not, the treatment group allocation for

as-treated analysis will be included in the efpeglenatide dose group that they are exposed for longer duration. In case of tie, highest dose group will be used.

- Participants, who premature discontinued study treatment during the titration phase, will be summarized in their planned treatment group for as-treated analysis too.
- Randomized participants will be excluded from the safety population only if there is documented evidence (ie, all study dates recorded as no medication taken) that participants have not taken the study treatment. If a participant is dispensed double-blind IMP and is lost to follow-up without any documented evidence, the participant will be considered exposed.

